## Known Potential Risks

By limiting the participants to two courses of treatment with ocrelizumab, participants are at higher risk of return of MRI or clinical disease activity. However, it is well within the standard practice to start patients with safer, but less efficacious disease modifying treatments and if the disease activity continued, to escalate to higher efficacy medications. Even in the case of more effective medications such as alemtuzumab, the standard practice is treatment with only two courses of the medication and retreatment if the disease activity returns. In this study, we will restart the treatment with ocrelizumab in patients who experience the return of the disease activity, a practice similar to escalation or retreatment which are standards of care.

Loss of privacy is another risk of participating in this study. Several mechanisms will help prevent loss of privacy. Access to the data will be limited to study personnel and the database will be password-protected. Furthermore, each member of the study team will be limited to only the data they need to perform their tasks so that privacy is protected as much as possible. Only study personnel who need to access the database will be given such access.

The risks associated with the study are minimal, and an adequate protection plan is in place; as such, the potential benefits exceed the potential risks. The participation of patients is completely voluntary; the alternative to the patients is to not participate in the study. Lack of participation will in no way compromise the relationship they have with their neurologists or the ongoing care they receive for their MS.

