### Schedule of events

Study visits will be conducted at the Johns Hopkins Outpatient Center (JHOC). Aside from obtaining informed consent for participation in the study and collecting peripheral blood mononuclear cells (PBMCs) and the NeuroQoL, all other procedures are part of the routine clinical and standard of care at Johns Hopkins MS Center. The only deviation from the standard of care in this study is stopping the ocrelizumab infusions after two courses. Study procedures are depicted in the following table (procedures in bold font are standard of care):

Tests and assessments	Screening visit	Infusion visits (month 0)	Month 3 (baseline)	Month 6	Month 12	Month 18	Month 24	Month 30
Informed Consent	X							
Verifying eligibility	X							

Medical history	X		X	X	X	X	X	X
Physical examination and vital signs assessment	X		X	X	X	X	X	X
Neurological examination (EDSS)	X		X	X	X	X	X	X
Blood work to assess eligibility for receiving ocrelizumab and its safety after the infusions	X		X	X	X			
OCT	X		X		X		X	
Brain MRI			X		X	X	X	X
Cervical/thoracic MRI			X		X		X	
NeuroQoL	X		X	X	X	X	X	X
Lymphocyte subset analysis			X	X	X	X		
Blood sample collection for storage and future analyses	X		X	X	X	X		
Blood draw and collection to be sent to Yale	X					X (or months 24)		
Ocrelizumab infusions		X 2 infusions two weeks apart		X 1 infusion				
Side effects assessment			X	X	X	X	X	X

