**Assessment of T and B-cell phenotypes and function at baseline and 18-24 months post-B-cell depletion**

The assessment T and B-cell phenotypes and function and analysis of the central and peripheral B-cell tolerance checkpoints, as well as measurement of cytokines will be done at Yale University. 30 milliliters of blood will be drawn from the participants before start of the treatment with ocrelizumab (at the screening visit) and 12 or 18 months after the second course of ocrelizumab infusion (month 18 or 24 of the study) and will be sent to Yale University for the analyses explained below.

We will investigate the T and B-cell phenotypes in the blood samples from the participants in the study, pre-treatment and after they repopulate their peripheral B-cells likely at either 18- or 24-months time points. We will follow the frequencies of  $CD3^+CD4^+CD25^{hi}CD127^{lo}FOXP3^+$  Tregs, circulating  $CD3^+CD4^+CXCR5^+PD-1^+$  Tfh cells increased in several autoimmune diseases, and other CD4+ and CD8+ naïve and memory T cell subpopulations. We will also assess the production of several cytokines including IL-2, IL-4, IL-6, IL\_10, IL-17, IL-21, IFN-gamma and TNF-alpha by Tregs and other T cell subsets after activating PBMCs with phorbol-12-myristate-13-acetate (PMA) and ionomycin for 4 hours in the presence of GolgiStop (BD Biosciences) and intracellular staining with specific monoclonal anti-cytokine antibodies as previously reported by our laboratory. Hence, we will determine if the abnormal production of IL-17 and IFN-gamma previously identified in Tregs from people with MS or their elevated Tfh frequencies are corrected after two courses of anti-B-cell deletion. In addition, we will assess *in vitro* the suppressive function of Tregs from people with MS before and after B-cell deletion. Indeed, Tregs from people with MS have been reported to display decreased suppressive function and we will therefore be able to determine if ocrelizumab can normalize Treg function and if this feature is associated with long-term disease suppression.

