#### [Analysis of the central and peripheral B-cell tolerance checkpoints](#)

Single CD19+CD10hiCD21-/loIgMhiCD27 new emigrant/transitional and CD19+CD10+CD21+IgM+CD27 mature naïve B-cells will be isolated from the blood of these patients before and after treatment and frequencies of polyreactive, HEp-2 reactive and anti-nuclear clones will be determined as previously described. In brief, Ig heavy and light chain genes will be amplified by RT-PCR and 20-30 immunoglobulin genes from single new emigrant/transitional and mature naïve B-cells will be cloned and expressed in vitro. Recombinant antibodies will be tested for HEp-2 reactivity and polyreactivity by ELISAs and anti-nuclear reactivity using indirect fluorescence assay on HEp-2 slides as previously described. Recombinant antibodies will be considered polyreactive when they recognized all three antigens tested individually (dsDNA, insulin, and LPS) using supernatants tested at 1 $\mu$ g/ml antibody concentrations and three 1:4 dilutions in PBS as reported. In HEp-2 and polyreactivity ELISAs, ED38 recombinant antibody will be used as positive control. Hence, we will determine if B-cell depletion can correct the impaired removal of developing autoreactive B-cells in the periphery of people with MS and is associated with disease suppression.

**Safety and adverse effect monitoring:** Potential participants will have lab work done (liver function tests, complete blood count, Hepatitis- B surface antigen, Hepatitis-B core antibody, HIV antibody, lymphocyte subset including CD19+ B-cells, total IgG and IgM and urine pregnancy test) as part of routine clinical care to assess for study eligibility and as the baseline for future comparison. Patients who are positive for Hepatitis-B surface antigen (HBsAg) or Hepatitis-B core antibody (HBcAb) will be excluded from participation.

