**Data safety monitoring committee (DSMB):** DSMB is not required for a small study using a medication that is FDA-approved for the condition, however, we will have the following treatment stop and study termination rules:

**Treatment stop rules:** Stopping the study is equivalent to restarting the B-cell depleting antibody (i.e. ocrelizumab) or another DMT, if there is medical contraindication to the continued use of ocrelizumab (e.g. development of allergic or severe infusion reactions during the last infusion). The followings are the criteria for restarting the DMT (stopping the study).

1. A clinical relapse, affecting optic nerves (with worst visual acuity of 20/50 or less) or causing motor weakness, ataxia, bladder or bowel symptoms. Pseudo-relapses are not uncommon among patients with MS. When in doubt, the PI will use MRI (similar to the standard of care) to confirm development of new lesions corresponding to patient's symptoms (based on the possible localization of the symptoms).
2. Development of two new T2 hyperintense lesions or two gadolinium enhancing lesions on any MRI after the baseline MRI. The baseline MRI was defined the MRI that is obtained three months after the first ocrelizumab infusion.

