## Statistical analysis

We will describe the demographic, clinical characteristics and MRI data of all participants before treatment with the B-cell depleting agent. We will report the proportion of participants who experience the primary endpoint of the study (return of the disease activity) and the time to failure event, using a Kaplan-Meyer curve. Proportion of patients with clinical relapse, new MRI activity or disability progression will separately be reported. Quality of life data will be analyzed using linear mixed effect models.

To look at the association between long-term response to B-cell depletion therapy and autoreactivity of B-cells at different stages of development, we will use logistic regression and Cox proportional hazards models with failure or time-to-failure event as the outcome variable and the above-mentioned proportion of auto-reactive B-cells at different stages of development and the change in proportions before and after treatment as the predictor variables. Failure event as defined in the Aim 1 is the return of disease activity after the third month post-first-infusion, objectively demonstrated by development of new T2 hyperintense lesions or Gd-enhancing lesions on the MRI or a clinical relapse that is confirmed with an objective change in the neurological examination or a corresponding new or enhancing lesion on the MRI that is obtained after the onset of symptoms.

Version: 2.0

Date: 3/8/2019

Using paired t-test, we will compare the frequency of autoreactive mature naïve B-cells, Treg and Tfh cells and cytokine production before treatment with ocrelizumab and after the B-cell repopulation.

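### Participants re-dosed before the month 18/24 tolerance draw may have no valid post-repopulation sample, and that loss depends on the outcome

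*Combined protocol and SAP*

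**What the plan says.** **Restart.** The Treatment stop rules, under safety monitoring, introduce the restart conditions with "The followings are the criteria for restarting the DMT (stopping the study"). The first is a relapse that affects the optic nerves beyond a set acuity, or that causes weakness, ataxia, or bladder or bowel symptoms. The second is "Development of two new T2 hyperintense lesions or two gadolinium enhancing lesions on any MRI after the baseline MRI". Known Potential Risks words the same action more broadly: "we will restart the treatment with ocrelizumab in patients who experience the return of the disease activity".

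**Sampling.** In the Schedule of events, the row "Blood draw and collection to be sent to Yale" is marked at screening and once afterwards, at month 18 or 24. The Outcomes section says these samples are taken "pre-treatment and after they repopulate their peripheral B-cells likely at either 18- or 24-months time points". A separate row, "Blood sample collection for storage and future analyses", covers screening and months 3, 6, 12 and 18. Lymphocyte subsets are scheduled at months 3, 6, 12 and 18.

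**Analysis.** A paired t-test compares autoreactive mature naïve B-cells, Treg and Tfh cells and cytokine production "before treatment with ocrelizumab and after the B-cell repopulation". Logistic and Cox models relate failure, or time to failure, to the autoreactive proportions and to their change.

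**Follow-up.** The section on discontinuation of study intervention keeps all treated participants under follow-up, and does not count a restart for breakthrough activity as discontinuation.

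**The concern.** The event that triggers re-dosing largely overlaps the primary failure event, but the tolerance draw is fixed by calendar. A participant who restarts first either has no post-treatment sample, if stopping the study ends sampling, or has one taken after re-dosing. A sample taken after re-dosing does not show B-cells that returned after two courses only. That re-dosing depletes them again is inferred from the Introduction, which describes repeat infusions as a way to keep the blood depleted. The Statistical analysis section has no rule for either case.

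The protocol's hypothesis links restored tolerance to suppressed disease. If that is right, the participants at risk of losing a sample are those least likely to be corrected. Their absence would make the Aim 2 comparison look more favourable, and would remove failures from the models meant to test the link.

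**Working it through.** **1. The plan's own figure.** Inputs from Sample size: 48.9 ± 3.06% in patients, 20.1 ± 0.9% in healthy donors, 10 before and 10 after, two-sided α = 0.05. Whether ± is an SD or an SEM is not stated.

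- Difference: 48.9 − 20.1 = 28.8 points.
- Read as SDs: SE = √((3.06² + 0.9²)/10) = 1.01, so 28.8/1.01 ≈ 28.6 and power is about 1.00.
- Read as SEMs from 20 subjects (assumption): SDs 13.68 and 4.02, SE = 4.51, 28.8/4.51 ≈ 6.4, and power is again about 1.00.

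The stated power above 90% is reproduced. In the less favourable reading, with no pre/post correlation, paired power is 0.998 with 8 pairs, 0.973 with 6, 0.914 with 5 and 0.762 with 4. Losing a few pairs does not threaten power. The issue is which pairs are lost.

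**2. When a restart can come before the draw.** The second course is at month 6.

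| Trigger | Effect on the tolerance sample |
|---|---|
| Month-12 MRI | Six months after the last dose, one usual dosing interval. Repopulation is expected only at month 18 or 24, so an early draw will often be unusable. |
| Month-18 MRI, draw at that visit | Not lost if blood is taken at the visit. |
| Month-18 MRI, draw deferred to month 24 | If deferred because B-cells had not returned, there was little to lose at month 18; otherwise recoverable. |
| Relapse or symptom-driven MRI before the draw | Recoverable if B-cells have returned by then. |
| Failure not meeting the restart criteria, or after the draw | Sample unaffected. |

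**3. Possible size of the bias.** Assume f of 10 participants fail with no change, the others change by −28.8, and l of the failures lose their sample.

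- Mean over all 10 = −28.8 × (10 − f)/10
- Mean over available pairs = −28.8 × (10 − f)/(10 − l)

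| f | l | All 10 | Available pairs | Overstatement |
|---|---|---|---|---|
| any | 0 | same | same | 0 |
| 1 | 1 | −25.92 | −28.80 | 2.88 |
| 2 | 1 | −23.04 | −25.60 | 2.56 |
| 2 | 2 | −23.04 | −28.80 | 5.76 |
| 3 | 1 | −20.16 | −22.40 | 2.24 |
| 3 | 2 | −20.16 | −25.20 | 5.04 |
| 3 | 3 | −20.16 | −28.80 | 8.64 |

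If failures correct by half (−14.4), each overstatement halves, to a range of 1.1 to 4.3. If failures correct as fully as the others, it is 0.

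**4. How often samples are lost.** The documents give no restart rate. If each participant had a 10% chance of restarting before the draw (assumption), the chance of losing none is 0.9¹⁰ = 0.35. At 20% it is 0.8¹⁰ = 0.11.

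**5. Association models.** A model on the post-treatment value or the change needs at least one failure with a valid post-treatment sample. Suppose 30% fail and 70% of failures restart before the draw (assumptions). Each participant is then a failure with a kept sample with probability 0.3 × 0.3 = 0.09. The chance that a trial has none is 0.91¹⁰ = 0.39, of which 0.7¹⁰ = 0.03 is trials with no failure at all. Models on screening proportions use blood drawn from everyone before treatment and keep every failure.

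**The case against.** **Much of the loss may not be recoverable.** This largely stands. At month 12 the B-cells will often not have returned, and the assay needs enough cells to clone "20-30 immunoglobulin genes from single new emigrant/transitional" and mature naïve B-cells. Against this, the safety section itself expects disease to return after B-cell reconstitution, so some restarting participants should have usable cells.

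**Drug-free blood and subset counts already exist at months 12 and 18.** True, and these are also MRI visits. But the stored blood is not assigned to the tolerance assay, is not tied to restart, misses events between visits, and could be paused under the COVID-19 changes.

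**The loss may be zero.** This stands. The phase II experience cited in the Introduction, one patient with enhancing lesions among more than 180 at 18 months, points to few failures, although dosing and endpoint differ. A single new lesion or a milder relapse is a failure but does not trigger restart.

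**Stronger readings that the documents do not support.**

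- *Every failure is re-dosed.* Known Potential Risks could suggest this, but the Treatment stop rules are narrower.
- *All association models collapse.* Only those needing the post-treatment value or the change lose events.
- *One retained failure gives a convincing association.* With 1 failure among 9, the smallest exact one-sided p-value is 1/9 = 0.11, and a full set of 10 gives at best 1/10. Under perfect separation the logistic estimate is not finite, so asymptotic p-values should not be relied on.
- *Failures are known to be uncorrected.* The protocol says only that correction may be responsible for suppression.

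**Conclusion.** The concern holds in a limited form. The plan allows a participant to be re-dosed before the only tolerance draw after treatment, requires no sample first, and has no rule for analysing that participant. The resulting loss depends on the outcome, and the paired comparison could overstate the mean correction if failures are less corrected.

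The size rests on assumptions: 0 if no sample is lost, and about 2 to 9 points of 28.8 with 1 to 3 wholly uncorrected failures among 10 and at least one lost. Even the extreme case leaves a mean change of −20.2, so the apparent direction of the result would not reverse. A reader might infer lost power or a biased primary endpoint. Neither follows: power holds down to five pairs under the plan's assumptions, and the primary failure time does not depend on this sample. In a 10-patient pilot where this is the secondary objective, it is a cheap improvement rather than a flaw in the main result.

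**What to change.** 1. In anyone restarting before the month 18/24 draw, take the 30 mL tolerance sample and a lymphocyte subset before the first re-dose, without delaying treatment and in place of the later draw. Assay it if B-cells have repopulated.
2. Do not count samples taken after re-dosing as post-repopulation samples.
3. Report how many participants, and how many failures, have a valid pair.
4. Add a sensitivity analysis assigning no change to restarted participants without a valid pair. This is a deliberately unfavourable bound, not a best estimate.
5. If no failure has a valid pair, report the association with change as not estimable.
6. Report time since last infusion with each sample.

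**Cost.** One re-timed draw and one subset count per restarted participant, one extra analysis and a few sentences. Because the draw replaces a planned one, the limit of 20 assayed samples is kept.

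**Downsides.** Early draws may yield too few cells; the subset count will help show this. Failures will also be sampled sooner after depletion than non-failures, so time since depletion becomes mixed with outcome. The association should be interpreted with item 6 in view.

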## Data management

Version: 2.0

Date: 3/8/2019

We will use REDCap (Research Electronic Data Capture) [<https://projectredcap.org/>], a secure web application to collect data, create the study database and access the data for analysis. Study coordinator will enter the data required by the protocol into the Electronic Case Report Forms (CRFs). The PI will assure that the data entered into CRFs are complete and accurate.

## Sample size

We selected to recruit 10 participants in this open-label, non-controlled study. We limited the number of participants for two reasons: The pre- and post-infusion analysis of B-cell tolerance is expensive and time-consuming, and we could accommodate the analysis of only 20 samples (10 pre and 10 post-infusions samples) during the proposed time of the study. We also wanted to make sure that we would observe a prolonged drug-free absence of disease activity in a subset of participants, before recruiting a larger group of patients for a potential larger study.

The sample size is supported by our previous studies of central and peripheral B-cell checkpoints in patients with autoimmune diseases and healthy control subjects in which we had found that the frequency of autoreactive mature naïve B-cells was  $48.9 \pm 3.06\%$  in patients and  $20.1 \pm 0.9\%$  in healthy donors. Assuming that the frequency of autoreactive cells among post-treatment repopulated B-cells will be similar to normal controls, our proposed sample size of 10 subjects per group before and after treatment would give us more than 90% power to detect a significant difference with an  $\alpha$  of 0.05 with a 2-sided Student's t-test. The analysis of each individual is very labor intensive and costly but fortunately, significant findings on the establishment of B-cell tolerance can be obtained with a relatively small number of subjects.

## Statistical analysis

We will describe the demographic, clinical characteristics and MRI data of all participants before treatment with the B-cell depleting agent. We will report the proportion of participants who experience the primary endpoint of the study (return of the disease activity) and the time to failure event, using a Kaplan-Meyer curve. Proportion of patients with clinical relapse, new MRI activity or disability progression will separately be reported. Quality of life data will be analyzed using linear mixed effect models.

To look at the association between long-term response to B-cell depletion therapy and autoreactivity of B-cells at different stages of development, we will use logistic regression and Cox proportional hazards models with failure or time-to-failure event as the outcome variable and the above-mentioned proportion of auto-reactive B-cells at different stages of development and the change in proportions before and after treatment as the predictor variables. Failure event as defined in the Aim 1 is the return of disease activity after the third month post-first-infusion, objectively demonstrated by development of new T2 hyperintense lesions or Gd-enhancing lesions on the MRI or a clinical relapse that is confirmed with an objective change in the neurological examination or a corresponding new or enhancing lesion on the MRI that is obtained after the onset of symptoms.

Version: 2.0

Date: 3/8/2019

Using paired t-test, we will compare the frequency of autoreactive mature naïve B-cells, Treg and Tfh cells and cytokine production before treatment with ocrelizumab and after the B-cell repopulation.

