## Investigational plan

### Study design

This is an open label, single-arm study of anti-CD20 antibody, ocrelizumab in people with relapsing MS. Patients who fulfill the eligibility criteria will undergo blood draw for collection of peripheral blood mononuclear cells (PBMC). Participants will receive two infusions of ocrelizumab (300 mg) two weeks apart and then six months later (one infusion of 600 mg of ocrelizumab), according to the medication label and the standard of care. Baseline brain, cervical and thoracic MRI will be obtained about 12 weeks after the first course of treatment. Participants will be followed with clinical visits at least twice a year (or more frequently, if needed) and brain MRI (every six months) and cervical and thoracic spine MRI, at least annually, up to two and a half years after the baseline MRI.

The trial design is depicted in the following diagram:

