### Changes in the study visits and procedures due to response to the CIVD-19 pandemic:

Considering the recent events (March 2020) surrounding the COVID-19 pandemic and JHU response, and the fact that our study participants can be particularly vulnerable to the infection with the novel coronavirus, we will implement the following changes in our study protocol to reduce the immediate hazard to our participants related to the risk of exposure to COVID-19:

- Follow-up visits, including Month 3, Month 6, Month 12 Month 18, Month 24 and Month 30 in-person visits can be replaced with telemedicine visits with the study PI.
- The medical history, symptom evaluation and side effects assessment components of the study visits will be conducted through the telemedicine visits.
- The physical examination, vital signs assessment, neurological examination, OCT and research blood sample collection for future analysis will be paused temporarily, as they would require an in-person visit and would pose a risk to the participants and the staff. They will be resumed as soon as possible, after the resumption of normal research activities at the JHU.
- The NeuroQoL quality of life assessment will be delivered to participants electronically. Secure Redcap surveys will be sent to the participants' email address. Results will be printed and filed in the study binders as usual.

Version: 2.0

Date: 3/8/2019

- The blood work to assess and monitor safety and adverse effects of the therapy, including lymphocyte subset analysis, will continue to be ordered and results will be reviewed electronically by the PI.
- Infusions of ocrelizumab: Ocrelizumab may theoretically increase the risk of infection with the novel coronavirus. Delaying the ocrelizumab infusions will be determined on a case-by-case basis by the PI.
- MRI Procedures: MRI studies may be delayed because of the delays in the ocrelizumab infusions.

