**Screening visit:** PI or designee will explain the study consent to study participants, and the study visit assessments will occur after the study participants sign the consent form. Screening visit procedures include review of eligibility criteria, physical exam, neurological examination, collecting vitals, blood work for assessing eligibility (liver function tests, complete blood count, Hepatitis- B surface antigen, Hepatitis- B core antibody, HIV antibody, lymphocyte subset including CD19+ B-cells, total IgG and IgM and urine pregnancy test) and blood draw (for collecting PBMCs), and completion of Neuro-QoL adult item banks. Study participants will be enrolled into the study after the study physician confirms participants' eligibility to move forward with the study.

Obtaining the B-cell depleting antibody (ocrelizumab) and all the subsequent study visits and MRIs are part of routine and standard clinical care. If the B-cell depleting medication is not approved by the participants' insurance policy, the patient will be excluded from the study.

**MRI procedures:** MRI scans will be performed at one of the Hopkins Radiology facilities at 3T. Conventional T2/FLAIR/T1-weighted images as well as post-contrast T1-weighted images of the brain will be obtained at months 3 (baseline), 12, 18, 24 and 30. Conventional T2/STIR/T1-weighted images as well as post-contrast T1-weighted images of the cervical and thoracic spinal cord will be obtained at months 3 (baseline), 12 and 24. Similar to the standard of care, brain, cervical or thoracic spine MRIs may be done as needed if the patient develop symptoms that could be suggestive for an MS relapse (based on the evaluation by a study neurologist). The MRI scans will be read by an attending radiologist at Johns Hopkins University, and these readings will be used for making decisions regarding the presence of new T2 or Gd-enhancing lesions suggestive for re-emergence of the radiological disease activity.

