## Outcomes:

**Primary outcome:** The primary endpoint (the failure event) of this study is the time to return of disease activity after the third month post-first-infusion, objectively demonstrated by development of new T2 hyperintense lesions or Gd-enhancing lesions on the MRI or a clinical relapse. A relapse is defined as new or worsening neurologic symptom(s) with an objective change on the EDSS of at least 1.5 points for participants with baseline EDSS scores of 0 or 0.5 and at least 1-point change for participants with EDSS of 1 or more, as determined by the *examining neurologist*. Symptoms must have been attributable to MS, last  $\geq 48$  hours, been present at normal body temperature, and preceded by at least 30 days of clinical stability. If a new or worsening neurological symptom did not fulfil the above-mentioned criteria, but was associated with a corresponding new or enhancing lesion on the MRI that is done in 30 days after the start of that symptom, it is still considered a clinical relapse.

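### Time to return of disease activity is analysed by ordinary Kaplan-Meier with no event-date rule, although symptom-free MRI failures are located only to within scan gaps of 6 to 12 months, so scan-dated times run late

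*Combined protocol and SAP*

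**What the plan says.** The Outcomes section defines the primary endpoint as "the time to return of disease activity after the third month post-first-infusion, objectively demonstrated by development of new T2 hyperintense lesions or Gd-enhancing lesions" on MRI, or a clinical relapse. The Statistical analysis section reports the proportion who fail and "the time to failure event, using a Kaplan-Meyer curve". It then reuses the outcome in "logistic regression and Cox proportional hazards models with failure or time-to-failure event as the outcome variable". Neither section gives a date rule for MRI failures, and neither mentions interval censoring.

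The documents describe scan timing in two ways:

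- Study design gives "brain MRI (every six months"), with spine MRI at least once a year.
- MRI procedures has "post-contrast T1-weighted images of the brain will be obtained at months 3 (baseline), 12, 18, 24 and 30", while images of the "cervical and thoracic spinal cord will be obtained at months 3 (baseline), 12 and 24". The Schedule of events table agrees with this version.

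Unscheduled scans are provided for only when symptoms suggest a relapse. The pandemic changes add that "MRI studies may be delayed because of the delays in the ocrelizumab infusions".

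**The concern.** The endpoint is worded as the return of disease, not its detection. A new lesion without symptoms arose at some unknown time between the last clean scan and the first positive one, so its failure time is interval-censored. An ordinary Kaplan-Meier curve needs a single date. The only exact date available for such a failure is that of the scan, which is the latest possible moment.

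The error therefore has one direction: the drug-free interval looks longer than it was, which is what the study hopes to show. There is no control arm to share the delay. Relapses, if dated at symptom onset, would be mixed on the same curve with scan dates that lag by months. The Cox model takes over the same times.

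**Working it through.** The plan gives no figure for this endpoint to reproduce; its only power statement concerns the B-cell comparison.

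**Inputs from the documents.** Brain scans at months 3, 12, 18, 24 and 30 give gaps of 9, 6, 6 and 6 months. Spine scans at months 3, 12 and 24 give gaps of 9 and 12 months, then none scheduled to month 30. N = 10, single arm.

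**Assumptions, because the documents give no failure rate.** Constant hazard from a start month s. True cumulative failure p by month 30 of 30% to 70%. New T2 lesions persist until the next scan. Each MRI failure is dated at the first scheduled brain scan on or after onset.

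**Formulas.**

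- Hazard: λ = −ln(1 − p)/(30 − s). Survival: S(t) = exp(−λ(t − s)) after s, and 1 before.
- True mean failure-free time, months 3 to 30: (s − 3) + p/λ.
- Scan-dated mean: 9·S(3) + 6·S(12) + 6·S(18) + 6·S(24), because the curve stays flat between scans.
- Overstatement = scan-dated minus true. Mean delay per failure = overstatement/p.

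| s | p | λ | True mean | Scan-dated mean | Overstatement | Mean delay |
|---|---|---|---|---|---|---|
| 3 | 30% | 0.01321 | 22.71 | 9 + 6(0.888 + 0.820 + 0.758) = 23.80 | 1.09 | 3.62 |
| 3 | 70% | 0.04459 | 15.70 | 9 + 6(0.669 + 0.512 + 0.392) = 18.44 | 2.74 | 3.92 |
| 12 | 30% | 0.01982 | 24.14 | 9 + 6(1 + 0.888 + 0.788) = 25.06 | 0.92 | 3.06 |
| 12 | 70% | 0.06689 | 19.47 | 9 + 6(1 + 0.669 + 0.448) = 21.71 | 2.24 | 3.20 |

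All times are in months. With s = 3, failures arising in months 3 to 12 are dated 4.6 to 4.8 months late on average. With s = 9 the mean delay is 2.8 months and the overstatement 0.8 to 2.0, because the earliest failures then wait at most three months for a scan.

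**Relapses dated at onset.** If a share f of failures carries no delay, the mean delay is multiplied by 1 − f. For f of 10% to 30% and s = 3, it runs from 0.7 × 3.62 = 2.5 to 0.9 × 3.92 = 3.5 months.

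**Six-monthly brain scans from month 3.** The mean delay would be 2.9 to 3.0 months. The wider first gap adds under one month; most of the delay comes from periodic scanning itself.

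**Median (s = 3).**

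| p | True median | Curve reads | S(18) |
|---|---|---|---|
| 30% | not reached by month 30 | not reached | 0.820 |
| 60% | 23.4 | 24 | 0.601 |
| 70% | 18.5 | 24 | 0.512 |
| 72% | 17.7 | 18 | 0.493 |

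The error jumps because the curve can cross 50% only at a scan month.

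**Proportion failed.** For lesions visible on brain MRI, the curve is right at every scan month. A spine-only lesion arising after month 24 meets no scheduled scan. If 15% of failures are spine-only (assumed), the month-30 shortfall is 0.15 × [S(24) − S(30)]:

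- s = 3: 0.15 × (0.758 − 0.700) = 0.9 points at p = 30%, and 0.15 × (0.392 − 0.300) = 1.4 points at p = 70%.
- s = 12: 1.3 to 2.2 points.

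Spine-only lesions arising in months 12 to 18 are likewise missed at month 18, but the month-24 spine scan picks them up.

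**The case against.** **Scan dating is not written down.** This stands. A reader might infer that the plan instructs the analyst to date MRI failures at the scan. It does not; the demonstrable gap is the missing date rule. The endpoint wording could also be read as time to objective demonstration, and for that quantity there is no bias. The plan does not name that quantity, however, and its hypothesis concerns suppression of disease.

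**Few failures are expected before month 12.** The second course is given at month 6, and the protocol expects B-cells to have returned by the month 18 or 24 sample. A constant hazard from month 3 may therefore overweight the nine-month gap. This is fair, and it is why the later starts are shown: the delay shrinks but does not disappear.

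**The large median error is a knife-edge case.** This also stands. A reader might take the 5.5-month error at 70% failure as typical, but at 72% it is 0.3 months and at 60% it is 0.6.

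**The pandemic clause need not widen any gap.** A reader might infer that delayed scans always enlarge the bias. If the first infusion is delayed, the whole scan sequence can move with it and no gap grows. The bias grows only where a scan slips relative to the one before.

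**The study is a pilot of 10, and Turnbull adds little.** Sampling error exceeds this bias, and no test or decision rests on the median. With common scan months, Turnbull matches Kaplan-Meier at those months and is undetermined between them. But sampling error can be shown by an interval, whereas this bias does not show and always flatters. Turnbull makes the undetermined stretches visible and handles scans that slip and relapses with onset dates.

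**Conclusion.** The concern holds for event times. With the scan date as the failure time, MRI-only failures are dated on average 3.6-3.9 months late if failures can start at month 3, and 3.1-3.2 months late if they start only after month 12. Mean failure-free time to month 30 is overstated by 1.1-2.7 or 0.9-2.2 months respectively. The median may be off by anything from under 1 month to about 5.5 months, depending on the failure rate. These sizes rest on an assumed constant hazard and 30-70% failure; only the direction is certain.

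A reader might go further and conclude that the reported proportion of failures is biased too. The documents do not support that. At month 30 it is affected only by spine-only lesions arising after month 24: about 1 percentage point at an assumed 15% share and up to 2.2 if failures start late, against 10 points for one participant.

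This should be corrected, but it does not undermine the study. Separately, Study design conflicts with the schedule table and MRI procedures on brain MRI timing, and that timing sets the resolution of the primary endpoint.

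**What to change.** In Statistical analysis:

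1. State the date rule: last clean and first positive assessments as bounds for MRI failures, onset date for relapses.
2. Estimate time to failure with the interval-censored nonparametric (Turnbull) estimator.
3. Report failure-free proportions at the scan months with exact intervals.
4. Treat the Cox outcome as grouped or interval-censored.
5. If a Kaplan-Meier curve is kept, label it time to detection.

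Elsewhere, reconcile Study design with the Schedule of events table and MRI procedures on MRI timing. If the tabulated schedule stands, state that scheduled spine imaging ends at month 24, so that scheduled imaging for the endpoint is brain only after that.

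No new data or participants are needed. The cost is a little more analysis work and a curve that looks less precise with 10 participants.
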